11.2 Antitumor Effect

11.2.1 Methods for Evaluation of Disease

All baseline evaluations should be performed on Cycle 1, Day 1 of initial therapy. Response will be assessed

CONFIDENTIAL

This document is confidential. Do not disclose or use except as authorized.

every cycle for the first 6 cycles and then every 3 months in the maintenance phase. Response will be assessed by M-protein quantification, protein electrophoresis and immunofixation from serum and a 24-hour urine collection. A serum sample for FreeLiteTM testing will be obtained. In addition, bone marrow aspiration and biopsy, as well as skeletal survey will be performed to determine overall response or confirm response.

The same method of assessment and technique should be used for disease measurement at baseline and during follow-up.

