1.3 Duration of Study

A treatment cycle is defined as 28 consecutive days.

Patients will receive 6 cycles of induction therapy followed by 6 cycles of maintenance therapy with lower doses of lenalidomide and no dexamethasone for a total of 12 months.

During maintenance, if a patient experiences biochemical progression ($\geq 25\%$ increase and an absolute increase of $\geq 0.5\text{g/dL}$ from their nadir in their serum or urine m-spike or FLC with no CRAB features attributable to MM progression) high-dose dexamethasone may be re-added to the combination at a dose of 40mg oral given on days 1, 8, and 15 of a 28 day cycle after discussion with the overall PI.

For all treatment cycles a $+\text{-} 7$ day window is allowed for Nivolumab. For hold and delay guidelines for lenalidomide and dexamethasone, please refer to Table 17. The treatment plan is designed to be administered on an outpatient basis, however if necessary, may be given as inpatient.

Patients will be followed for up to three years after discontinuation of therapy.

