10. STUDY CALENDAR

Screening evaluations are to be conducted within 28 days of registration. Imaging assessments that are completed within 6 weeks of registration need not be repeated at screening. If a patient had a bone marrow core biopsy done within 6 weeks of registration, a bone marrow aspirate sample need only be collected for baseline and research purposes. Baseline assessments are to be conducted on C1D1 of initial therapy and should be considered separate from screening evaluations. If screening assessments are performed within 7 days of C1D1, disease assessments (SPEP, UPEP, Immunofixation, Free light chain assay, quantitative immunoglobulins) do not need to be repeated. Lab values that are used to prove eligibility for patients with progressive (evolving) smoldering myeloma do not need to be within the 21 day window, but screening values will need to be established in window. All assessments must be performed prior to administration of any study medication. See below for detailed scheduled of assessments. Study medications will be administered according to the schedule and guidelines outlined in Section 5.

	Pre-registration		Cycles 1-12 (28 days) ³				Follow-Up
Tests and procedures	≤ 28 days prior to registration	≤ 21 days prior to registration	Day 1 of cycles 1-6 ¹	Day 1 of cycles 7-12	Cycle 7 Day 1 and to confirm CR ⁸	End of Treatment ¹⁸	Every 3 Months ¹¹
History and exam, height, weight. Performance Status	X		X	X		X	X
Response Assessment ¹⁷			X	X		X	X
Toxicity Notation			X	X		X	
Hematology group (WBC w/ diff, PLT, Hgb, ANC)		X	X	X		X	X
Chemistry ⁴		X	X	X		X	X
Direct & total bilirubin ²		X	X	X		X	
Free light chain assay		X	X	X		X	X
Serum and Urine Immunofixation (SPEP and UPEP) with quantitative immunoglobulins ⁹		X	X	X		X	X
β2M, CRP, LDH ¹⁶		X	X	X		X	
TSH, Free T4, Free T3		X	X	X		X	
Metastatic Bone Survey and Spine MRI OR PET/CT only ¹⁰	X					X	
EKG ¹⁵		X				X	
Serum pregnancy test ¹²		X					
Unilateral bone marrow aspirate and biopsy ⁵	X				X	X	
Research bone marrow aspirate ⁶	X ⁵				X ⁶	X ⁶	
Research Blood ⁷	X ⁷		X ⁷	X ⁷	X ⁷	X ⁷	
Buccal Swab ¹³	X						

1- Cycle 1, Day 1 laboratory values need to meet eligibility criteria

2- Direct bilirubin to be obtained if total bilirubin is abnormal.

3- Scheduling allows for +/- 7 days all cycles.

4- Chemistry includes sodium, potassium, chloride, bicarbonate, bun, creatinine, calcium, glucose, albumin, ALT (SGPT), total protein, AST (SGOT), total bilirubin, magnesium, and phosphorus.

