5- A bone marrow biopsy is required within 6 weeks of registration. A bone marrow aspirate for clinical and research purposes is required pre-treatment and may be performed up to 28 days prior to registration. Both core and aspirate are required any time during the course of the study to confirm CR, and is also required at C7D1

6- Research bone marrow aspirate and biopsy at the same time as clinically indicated bone marrow biopsy and to confirm response.

CONFIDENTIAL

This document is confidential. Do not disclose or use except as authorized.

Local Protocol #: 16-242

Version Date: 23 January 2018

7- Peripheral blood samples for correlative studies may be done at any time pre-treatment, though baseline and C1D1 samples should be considered separate time points.

8-If C7D1 or confirmation of response BM aspirate and core biopsy was performed within 3 weeks of either timepoint, the procedure need not be repeated. At minimum, an aspirate sample is required

9- Disease assessment/response assessment is required each Day 1 starting with C2-If the participant's disease response is not followed primarily via a UPEP (24 hour urine collection) and Urine immunofixation, these tests may be done only at screening, end of treatment, and every 3 months during treatment.

10-A CD of scans at screening and end of treatment is required to be sent to the lead site for central review. Screening scans should be sent with the eligibility packet to the lead site- This requirement includes a full body skeletal survey in addition to spinal MRI OR the patient may have only a low dose PET CT

11- Follow-up should occur every 3 months (+/- 14 days) for up to 3 years after end of treatment.

12- Women of child-bearing potential must abide by revlimid REMS procedures and may require additional pregnancy testing as described in section 3.1.7.

13- Buccal swab may be collected at any time throughout the study but should be collected pre treatment on C1D1

14- Thyroid labs are required at screening, C3D1, C6D1 and every 3 cycles thereafter, at end of treatment, and at any time that it is clinically indicated

15- Alert Overall PI immediately if there is concern for cardiac toxicity (At minimum, the following should be performed: cardiology consult, EKG, echocardiogram, and labs CPK and troponin; refer to section 6.2.7 for more details)

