16- B2M, CRP, and LDH are required at screening, C3D1, C6D1 and every 3 cycles thereafter, at end of treatment, and at any time that it is clinically indicated

17- A disease response assessment will be required at every Day 1 starting with Cycle 2, end of treatment, and every follow up visit (q3 months) until completion, withdrawal, disease progression, subsequent therapy or death

18- All end of treatment assessments will be performed within 14 days from the date that the decision to end treatment was made by the study team

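### Section 11.2.1 sets 3-monthly response assessment in maintenance while the study calendar requires it every cycle, so M-protein and light-chain progression and response confirmation can be dated up to about two months apart.

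*Combined protocol and SAP*

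**What the plan says.** Section 11.2.1 gives the response schedule as "every cycle for the first 6 cycles and then every 3 months in the maintenance phase".

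Section 10 gives a different one:
- The calendar marks Response Assessment, free light chain assay, and serum and urine electrophoresis with immunofixation under Day 1 of cycles 7-12.
- Footnote 9: "Disease assessment/response assessment is required each Day 1 starting with C2".
- Footnote 17: "A disease response assessment will be required at every Day 1 starting with Cycle 2, end of treatment", and then every follow-up visit. The 3-month interval in that footnote belongs to follow-up after treatment.

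Footnote 9 has one on-treatment exception. For participants whose disease is not followed mainly by 24-hour urine, the urine tests are relaxed: "these tests may be done only at screening, end of treatment, and every 3 months during treatment". Serum tests and the response assessment itself are not relaxed.

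The endpoints rest on these visits. Sections 11.1, 11.2.2 and 11.2.2.1 require responses to be confirmed, with two consecutive assessments. Section 11.2.4.1 ends duration of response at first documented progression or death. Section 11.2.4.3 censors time to progression at the last disease assessment for patients alive without progression.

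**The concern.** For cycles 7-12 the plan contains two assessment intervals, one more than three times the other. The urine exception does not reconcile them, because it covers only some tests in some participants. Rises in M-protein and free light chain count as progressive disease in Sections 11.2.2.1 and 11.2.2.2, and a free light chain ratio of 100 or more is a myeloma-defining event in Section 11.1. They are seen only when the tests are done. The biochemical progression described for maintenance in Sections 1.3 and 5.1 is read from the same tests.

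The trial has several sites, and Section 11.2.6 plans no central review of response, so nothing downstream would harmonise sites that read different pages. It is also single-arm, so a detection delay is not cancelled by a control arm on the same schedule. The sparser interval pushes observed time to progression and progression-free survival towards longer values.

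**Working it through.** The plan states no figure on this point, so the check compares the two schedules by date arithmetic.

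**Inputs**
- Cycle length (Section 1.3): "A treatment cycle is defined as 28 consecutive days".
- Phases (Section 1.3): "6 cycles of induction therapy followed by 6 cycles of maintenance therapy".
- Visit window (Section 10, footnote 3): "Scheduling allows for +/- 7 days all cycles".
- Assumptions: 3 months = 3 × 30.44 = 91.3 days; C1D1 is day 0; the first maintenance assessment under 11.2.1 is at C7D1; End of Treatment is at day 336.

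**Number of assessments**
- Maintenance runs from day 6 × 28 = 168 to day 12 × 28 = 336, which is 168 days.
- Calendar: days 168, 196, 224, 252, 280 and 308, so 6.
- Section 11.2.1: days 168 and 168 + 91.3 = 259, so 2. The next, day 351, falls after Cycle 12. Counting instead from C6D1 (day 140) gives days 231 and 323, again 2.
- Both texts share the End of Treatment assessment, at about day 336 and up to day 350 with the 14 days in footnote 18.

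**Delay in documenting an M-protein or light-chain change**
- Interval ratio: 91.3 / 28 = 3.3.
- Largest extra delay: 91.3 − 28 = 63 days. A change just after day 168 is seen on day 196 by the calendar and on day 259 by 11.2.1.
- Mean extra delay, with onset uniform within the interval: 91.3/2 − 28/2 = 45.7 − 14 = 32 days.
- The half-interval mean ignores the shared End of Treatment visit. Placing onsets evenly over days 168-336:

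| Onset (days) | Seen, calendar | Seen, 11.2.1 | Extra delay |
|---|---|---|---|
| 168-196 | 196 | 259.3 | 63.3 |
| 196-224 | 224 | 259.3 | 35.3 |
| 224-252 | 252 | 259.3 | 7.3 |
| 252-259.3 | 280 | 259.3 | −20.7 |
| 259.3-280 | 280 | 336 | 56 |
| 280-308 | 308 | 336 | 28 |
| 308-336 | 336 | 336 | 0 |

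Weighted mean: [28 × (63.3 + 35.3 + 7.3) − 7.3 × 20.7 + 20.7 × 56 + 28 × 28] / 168 = about 28 days. So 32 is a fair round figure, slightly high.
- The ±7-day window does not close a 63-day gap.

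**How many patients could be affected**
- Assume exponential progression at the design rates in Section 13.1 (50% and 70% progression-free at 2 years, 39 patients). Maintenance covers 168/365.25 = 0.46 to 0.92 years.
- At 50%: 39 × (0.5^0.23 − 0.5^0.46) = 39 × (0.853 − 0.727) = 4.9.
- At 70%: 39 × (0.7^0.23 − 0.7^0.46) = 39 × (0.921 − 0.849) = 2.8.
- So about 3 to 5 progressions would fall in maintenance, by any criterion and at any site.

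**Effect at 2 years**
- End of Treatment is at 336/30.44 = 11.0 months. After that both texts give visits at about 14, 17, 20 and 23 months. The schedules have therefore coincided for about a year before the primary endpoint is read.

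**The case against.** The strongest case on the other side is that the calendar is the operative schedule. Section 10 presents itself as the detailed schedule, the tests are marked there on every Day 1, and Section 6.5 sends sites to it when lenalidomide or dexamethasone is held. A site would have to skip required tests to follow 11.2.1. This makes divergence less likely, but Section 6.5 covers held doses and is not a general precedence rule, so the contradiction stands.

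Several limits on the consequence also stand:
- A reader might infer that a response first seen at the second 3-month visit can never be confirmed. The documents do not support that. The End of Treatment visit includes a response assessment, follow-up visits do too, and Section 11.2.2.1 accepts confirmation at any time before new therapy. Confirmation comes later; it would be lost only if new therapy or dropout came first.
- The 28-day confirmation gap is not general. Complete response needs negative urine immunofixation, and under footnote 9 the repeat urine test may be about 3 months away even on the calendar. The modified EBMT criteria in Section 11.2.2.3 require six weeks (42 days), so one cycle is too short for them.
- Calcium, creatinine and hemoglobin are tested every Day 1 under both texts, so these CRAB criteria are much less exposed.
- Accrual closed and nivolumab was stopped in September 2017, while this version is dated January 2018. The documents do not say how many participants still had maintenance visits ahead, so the prospective gain may be small.

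**Conclusion.** The contradiction is in the current text and nothing in the documents resolves it. It is an internal inconsistency, wrong as written, rather than a design choice, and it is minor. During cycles 7-12, progression by M-protein or free light chain and confirmation of response can be documented up to about 63 days later, and about 32 days later on average, at a site following 11.2.1. For time to progression and progression-free survival the bias is towards longer times. For duration of response the direction is less certain, because the first response can also be seen later. The size is modest: some 3 to 5 of 39 patients would be expected to progress in this window, and only those progressing by these markers at a site using the sparser schedule are affected.

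A reader might also infer that the primary result is at risk. It should be essentially unchanged, because the 2-year rate is binary and both texts give the same visits from about month 11.

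These figures rest on a first maintenance assessment at C7D1, uniform onset within intervals and, for the patient count, exponential progression. The documents do not show which schedule any site used.

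**What to change.** Replace the maintenance part of the sentence in Section 11.2.1 with the calendar rule: response assessed on Day 1 of every cycle from Cycle 2 to Cycle 12, at End of Treatment, then every 3 months in follow-up. Keep the footnote 9 exception and say that it applies to urine tests only. For maintenance assessments already done, report the interval actually used, by site, alongside the time-to-event and response results.

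The cost is one sentence in the protocol and one descriptive table in the report. The serum tests are already scheduled on those days, so no visit or procedure is added.

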11.2.2 Response Criteria

A confirmation measurement for disease response assessments is required in this protocol.

11.2.2.1 International Myeloma Working Group Response Criteria

Response criteria for all categories and subcategories of response except CR are applicable only to patients who have 'measurable' disease, as defined in Section 11.1.1. All response categories require two consecutive assessments made at any time before the institution of any new therapy; all categories also require no known evidence of progressive or new bone lesions if radiographic studies were performed. Radiographic studies are not required to satisfy these response requirements.

Response	Criteria for Response
Stringent CR (sCR)	
CR as defined below plus normal free light chain ratio and absence of clonal cells in bone marrow* by immunohistochemistry or ** immunofluorescence.
 
*Confirmation with repeat bone marrow biopsy is not needed.
 
**Presence/absence of clonal cells is based upon the k/λ ratio. An abnormal k/λ ratio by immunohistochemistry and/or immunofluorescence requires a minimum of 100 plasma cells for analysis. An abnormal ratio reflecting presence of an abnormal clone is k/λ of > 4:1 or < 1:2.

Complete Response (CR)	
Negative immunofixation on the serum and urine and disappearance of any soft tissue plasmacytomas and ≤5% plasma cells in bone marrow.
 
*Confirmation with repeat bone marrow biopsy is not needed.

Very Good Partial Response (VGPR)	
Serum and urine M-protein detectable by immunofixation but not on electrophoresis or 90% or greater reduction in serum M-protein plus urine M-protein level <100mg per 24 hours.

Partial Response (PR)	≥ 50% reduction of serum M-protein and reduction in 24-h urinary M-protein by > 90% or to < 200mg per 24 hours. If the serum and urine M-protein are
------------------------------	--

CONFIDENTIAL

This document is confidential. Do not disclose or use except as authorized.

	unmeasurable, a $\geq 50\%$ decrease in the difference between involved and uninvolved free light chain levels is required in place of the M-protein criteria (definition of measurable disease in Section 10.2.3). If serum and urine M-protein are unmeasurable, and serum free light assay is also unmeasurable, $\geq 50\%$ reduction in plasma cells is required in place of M-protein, provided baseline bone marrow plasma cell percentage was $\geq 30\%$. In addition to the above listed criteria, if present at baseline, a $> 50\%$ reduction in the size of soft tissue plasmacytomas is also required.
Stable Disease (SD)	Not meeting criteria for CR, VGPR, PR or progressive disease. This is not recommended as an indicator of response; stability of disease is best described by providing the time to progression estimates.
Progressive Disease (PD)	$> 25\%$ increase of serum M-protein (which must also be an absolute increase of ≥ 0.5 g/dL) and/or urine M-protein (which must also be an absolute increase of ≥ 200 mg/24hr). If serum and urine M-protein are unmeasurable, there must be an absolute increase of ≥ 10 mg/dL between involved and uninvolved FLC levels. PD is also measured by an absolute increase in bone marrow plasma cells $\geq 10\%$. In addition to the above listed criteria, progression may also be measured by a definite development of new bone lesions or soft tissue plasmacytomas or definite increase in the size of existing bone lesions or soft tissue plasmacytomas or development of hypercalcemia (corrected serum calcium ≥ 11.5 mg/dL or 2.65 mmol/L) that can be attributed solely to the plasma cell proliferative disorder.

11.2.2.2 FreeLite™ Disease Response Criteria

Response	Criteria for Response
Complete Response (CR)	For those patients being followed by serum free light chain (and NO measurable serum or urine M-spike), which were immunofixation negative at enrollment, normalization of serum free light chain ratio. Normalization is defined as the serum free light chain ratio being within the normal range. If the serum free light chain ratio is not within the normal range, but the individual kappa and lambda light chain values are within normal range, this may be considered CR.

Partial Response (PR)	If only measurable parameter is serum immunoglobulins free light chain (FLC), EITHER
------------------------------	---

CONFIDENTIAL

This document is confidential. Do not disclose or use except as authorized.

	
of the following changes qualify as partial response:
 
• $\geq 50\%$ decrease in the difference between involved and uninvolved FLC levels from the lowest response level, which must also be an absolute increase of at least 10 mg/dL OR• $\geq 50\%$ decrease in the level of involved FLC AND a $\geq 50\%$ decrease in the ratio of involved/uninvolved FLC from the lowest response level.
Progressive Disease (PD)	
If only measurable parameter is serum immunoglobulins free light (FLC), EITHER of the following qualify as progression:
 
• $\geq 50\%$ increase in the difference between involved and uninvolved FLC levels from the lowest response level, which must also be an absolute increase of at least 10 mg/dL OR• $\geq 50\%$ increase in the level of involved FLC AND a $\geq 50\%$ increase in the ratio of involved/uninvolved FLC from the lowest response level.

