11. MEASUREMENT OF EFFECT

11.1 Development of symptomatic disease

In this study, the final endpoint is development of symptomatic MM that requires therapy.

This is defined as one of the following criteria (≥ 1 CRAB Criterion and Myeloma Defining Events ≥ 1 MDE):

- Increased calcium levels (corrected serum calcium >0.25 mmol/dL above the upper limit of normal or >2.75 mmol/dL) due to myeloma
- Renal insufficiency (attributable to myeloma);
- Anemia (Hb 2g/dL below the lower limit of normal or <10 g/dL) due to myeloma
- Bone lesions (lytic lesions or generalized osteoporosis with compression fractures)
- Myeloma Defining Events (MDE) as follows:
 - Clonal bone marrow plasma cell percentage $\geq 60\%$ ⁷
 - An abnormal FLC-ratio ≥ 100 (involved kappa) or <0.01 (involved lambda)⁸
 - 2 or more focal lesions on MRI or PET-CT studies^{9,10}

For measurement of response:

The disease response will be assessed using criteria based on the International Myeloma Working Group Uniform Response Criteria in Section 11.2.2.1 or FreeLite™ Disease Response Criteria in Section 11.2.2.2.

Disease response by the Modified EBMT Response Criteria in Section 11.3.2.3 will also be collected on participants as a secondary measure.

The same method of assessment and technique should be used for disease measurement at baseline and during follow-up. Disease response should be confirmed by two consecutive assessments.

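### The FreeLite partial-response row contradicts itself and uses a progression reference level, so PR in light-chain-only patients may be missed, delayed or scored inconsistently

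*Combined protocol and SAP*

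**What the plan says.** Section 11.2.2.2 (FreeLite criteria) applies to patients in whom FLC is the only measurable parameter. Its PR row says that either "of the following changes qualify as partial response":

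- **Option 1:** a fall of at least 50%, worded as a "decrease in the difference between involved and uninvolved FLC levels from the lowest response level, which must also be an absolute increase" (10 mg/dL or more).
- **Option 2:** a fall of at least 50% in the involved FLC, together with a 50% or greater "decrease in the ratio of involved/uninvolved FLC from the lowest response level".

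The progressive-disease row of the same table asks for a 50% or greater "increase in the difference between involved and uninvolved FLC levels from the lowest response level, which must also be an absolute increase of at least", with the threshold again set to 10 mg/dL. The reference level and the absolute-increase condition are the same as in option 1 of the PR row.

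The IMWG table in Section 11.2.2.1 has its own rule for patients whose serum and urine M-protein are unmeasurable: a 50% or greater "decrease in the difference between involved and uninvolved free light chain levels is required in place of the M-protein criteria". It carries no absolute-increase condition and does not refer to a lowest level.

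Section 11.1 says that response is assessed by the "International Myeloma Working Group Uniform Response Criteria in Section 11.2.2.1 or FreeLite™ Disease Response Criteria in Section 11.2.2.2". It gives no order of precedence. Section 13.1.2 defines the objective response rate as PR or better by modified IMWG criteria.

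**The concern.** A response rule should describe a fall from where the patient started. Here, text that suits progression (a rise, counted from the best level reached) sits in the PR row. Option 1 therefore cannot be met. Option 2 depends on what the lowest response level means for a patient who has not yet responded, and the table does not define it.

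Light-chain smoldering patients may enrol (Section 3.1.2), every response needs two consecutive assessments (Sections 11.1 and 11.2.2.1), and no central review of response is planned (Section 11.2.6). Two assessors could score the same FLC course differently, and nothing in the plan would reconcile them.

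Response rate and duration of response are secondary objectives (Section 1.5). A missed PR lowers the rate and removes that patient from the duration analysis. A delayed PR moves the start of that patient's duration later.

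**Working it through.** **The plan's own figure.** Section 13.1.2 states that the exact 90% confidence interval for the response rate is no wider than 28% with 39 patients. The Clopper-Pearson interval, computed for every count from 0 to 39, has its greatest width, 0.2814, at 20 responders. This agrees with the plan to the nearest point and does not depend on how PR is worded.

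**Option 1.** Let D0 > 0 be the reference difference (involved minus uninvolved FLC) and D1 the current one, in mg/dL.

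- A fall of at least 50%: D1 − D0 ≤ −0.5 × D0, which is below 0.
- An absolute increase of at least 10: D1 − D0 ≥ 10.

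Both cannot hold. A grid of 9,996 pairs of reference and current FLC values gave no case that met option 1.

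**Option 2 and the IMWG rule.** Two illustrative courses (assumed values) start at involved FLC 60 mg/dL, with uninvolved FLC constant at 1 mg/dL. With uninvolved FLC at 1, the ratio falls by the same percentage as the involved FLC. The running low is the lowest earlier value, counting baseline. The IMWG row names no reference level, so it is read here against baseline (difference 60 − 1 = 59).

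| Course | Value | Fall from running low | Option 2, running low | Fall from baseline | Option 2, baseline | IMWG difference from baseline |
|---|---|---|---|---|---|---|
| Gradual | 42 | 18/60 = 30.0% | no | 30.0% | no | 18/59 = 30.5%, no |
| Gradual | 30 | 12/42 = 28.6% | no | 30/60 = 50.0% | yes | 30/59 = 50.8%, yes |
| Gradual | 22 | 8/30 = 26.7% | no | 38/60 = 63.3% | yes | 38/59 = 64.4%, yes |
| Gradual | 16 | 6/22 = 27.3% | no | 44/60 = 73.3% | yes | 44/59 = 74.6%, yes |
| Fast | 20 | 40/60 = 66.7% | yes | 66.7% | yes | 40/59 = 67.8%, yes |
| Fast | 18 | 2/20 = 10.0% | no | 42/60 = 70.0% | yes | 42/59 = 71.2%, yes |

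Against a running low, the gradual course never reaches PR despite a 73% fall. The fast course qualifies once, but the confirming value fails because a second halving would be needed. Against baseline, both courses are confirmed PRs under option 2 and under the IMWG rule.

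**Size per patient.** 1/39 = 2.6 percentage points of response rate for each misclassified patient.

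**The case against.** The strongest reply is that a patient can still be scored PR.

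- Option 2 is a true alternative without the contradiction, and a steep fall meets it.
- The lowest response level need not mean a running low. Footnote d to the EBMT table (Section 11.2.2.3) falls back to the baseline value when there is no earlier confirmed response. On that reading option 2 works.
- Section 13.1.2 bases the response rate on modified IMWG criteria, and the IMWG table has a usable FLC rule.

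The first point stands in full. A reader might infer that FLC-only patients cannot be scored PR at all; the documents do not support that.

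The second stands in part. The footnote concerns increases and belongs to another table, so it shows a sensible reading without settling the matter.

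The third also stands in part. The modified IMWG criteria are not defined, and Section 13.1.2 also reports minimal response, a category found only in the EBMT table. The IMWG table cites Sections 11.1.1 and 10.2.3 for measurable disease, and neither appears in the text provided. With Section 11.1 allowing either table, the FreeLite row is not clearly excluded from the response-rate analysis.

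**Conclusion.** The PR row is a wrong rule in an operative table and should be corrected. Option 1 is impossible, both options use a progression reference, and the row conflicts with the IMWG rule for the same patients. Applied literally, it can miss or delay a PR or produce inconsistent scoring.

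A reader might go further and infer that the response rate is understated by a definite amount. If 2 to 8 of 39 patients were FLC-only, 79% of them truly responded (the post-induction figure in Section 2.6, from a different regimen) and every such response was lost, the rate would fall by 0.79 × 2/39 = 4.1 to 0.79 × 8/39 = 16.2 points. The documents do not support this. They give no count of FLC-only patients. Light-chain smoldering patients who qualify through urine excretion of at least 500 mg/24 hours (Section 2.5) would ordinarily have a urine marker to follow. Option 2, the IMWG rule and CR all remain available.

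The supportable size is about 2.6 points per misclassified patient, assuming 39 are analysed. Accrual stopped under the September 2017 hold (Section 1.1); with fewer patients, each one counts for more. The primary 2-year progression-free rate and its 24-of-39 rule do not use PR.

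**What to change.** 1. In the PR row of Section 11.2.2.2, delete the condition requiring an absolute increase of at least 10 mg/dL.
2. In both options of that row, replace the lowest response level with baseline as the reference. Leave the progressive-disease row as it is.
3. State in Sections 11.1 and 13.1.2 that FLC-only patients are scored in the response-rate analysis by the IMWG FLC rule: a decrease of at least 50% in the involved-minus-uninvolved difference from baseline, with which the corrected FreeLite row agrees.

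The cost is one table row and a sentence in each of two sections. No new data are needed. It can be done before the final analysis, and any FLC-only response already scored from the FreeLite row can be rechecked against the FLC values collected.
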